6.1. Statistical Endpoints and Hypothesis

Primary endpoint:

To show superiority of the addition of oxaliplatin to neoadjuvant chemoradiotherapy (N-CRT) and to 5-FU-based adjuvant chemotherapy (experimental arm) in comparison to standard N-CRT followed by adjuvant 5-FU monotherapy (control arm) in terms of DFS within three years of follow-up (primary endpoint).

DFS is defined as the time frame between day of randomization and the first day of occurrence of at least one of the following items:

- R2 resection
- local relapse following R0 or R1 resection
- evidence of distant metastasis
- death of the patient

If none of the aforementioned events occur for a randomized patient within the follow-up time, the patient will be censored at the first day at which at least one of the following events occur:

- end or truncation of the study
- study dropout by patient's initiative

The null hypothesis of this study is that there is no statistically significant difference between the experimental and the control arm.

Secondary endpoints were classified as:

- R0 resection rate, circumferential resection margins, quality of TME-surgery
- TNM-classification, number of investigated lymph nodes after quality controlled TME-surgery
- proportion of sphincter-preserving surgical procedures
- tumor regression grading
- cumulative incidence of local relapses and distant metastasis
- overall survival after five years
- acute toxicity of radio- and chemotherapy according to CTC criteria
- late toxicity of radio- and chemotherapy

6.2 Sample Size Calculation for the Entire CAO/ARO/AIO-04 Study

In the experimental arm (i.e. the neoadjuvant chemoradiotherapy with 5-FU) within the precursor study CAO/ARO/AIO-94, DFS after three years was 74.9% (Fig. 1). This treatment now serves as control arm and as the basis for sample size calculation of the CAO/ARO/AIO-04 study. When assuming a 82% DFS for the intensified chemoradiotherapy with oxaliplatin and protocol violations of 5% in both treatment arms, about 1200 patients (600 in each arm) will be necessary to achieve a power of 80% at 5% significance level with the log-rank test (Fig. 2 and Figure 3). Sample size estimation was performed as described in Lachin & Foulkes (1986) [2].

[figure not shown]

Fig. 1 Disease-free survival for 406 patients in the neoadjuvant arm (i.e. chemoradiotherapy with 5-FU) of the precursor CAO/ARO/AIO-94 study (Sauer 2004 [3]). Percentages and absolute numbers of patients at risk for the considered time points are indicated.

[figure not shown]

Fig. 2 Sample size required to achieve 80% power for the log-rank test with a recruitment period of 3 years and minimal follow-up of 2 years in dependence on disease-free survival in the experimental arm and the rate of protocol violations.

[figure not shown]

Figure 3 Power of log-rank test at a significance level of 5% in dependence on disease-free survival for n=1200 patients.

6.3 Analysis cohorts

The 'intent-to-treat' population refers to all randomized patients with the study arm defined by randomization, regardless of protocol violations, stop of treatment, or time of follow-up.

The 'per-protocol' population is composed of all patients who started therapy. The patients will be analyzed in the therapy arm where they were actually treated, regardless of randomization. For the interim safety analyses all randomized patients will be considered who started therapy.

6.4 Statistical Analysis

6.4.1 Testing the Primary Endpoint

The hypothesis concerning the primary endpoint, as defined in Section 6.1, is based on the 'intent-to-treat' population assessed by log-rank statistics. The reference distribution under the null hypothesis of equal DFS in both arms will be derived from the asymptomatic conditional distribution of the log-rank statistics for each participating center and in relation to the most prognostic factor, the lymph node status at time of randomization. That corresponds to stratification according to participating centers and dichotomous lymph node status. The effect size is defined by the point estimator with 95% confidence interval of the hazard ratio. If the null hypothesis can be rejected at level of 5%, the experimental treatment will be established. The primary endpoint will be visualized by Kaplan-Meier survival curves.

6.4.2 Interim Analyses

Since planning of the required sample size harbors uncertainties both for methodological reasons such as assumptions of distributions as well as for the estimation of the effect size, a sequential procedure enabling adaption of the study protocol in terms of sample size makes sense. An interim analysis, which is conducted upon minimal follow-up time for half of the patients, could be carried out at the soonest at 3.5 years after start of study, i.e. when the recruitment phase is completed and the last patients have been treated. Therefore, interim analyses have to be restricted on the confirmatory analysis of secondary endpoints referring to treatment safety. These analyses will be performed annually, starting one year after start of study and will result in study stop if a relevant increase in toxicity in the experimental arm is observed (see Section 6.4.4).

In order to postulate superiority of the experimental arm as early as possible and to be able to offer this treatment to newly diagnosed patients, an interim analysis can be conducted if at least 50% of the recruited patients have completed the minimal follow-up time of two years. In this case, the nominal level of 5% will be divided according to Kim and DeMets 1987 [4]. Thereby, data are based on the proportion of patients with completed follow-up time (DeMets 1985 [5], DeMets 1989 [6]).

6.4.3 Explorative Analyses

All analyses of secondary endpoints including interim safety analyses are of explorative nature, in particular, no adjustment for multiple testing will be performed. Censored secondary endpoints will be analyzed analogously to the method described in Section 6.4.1. Nominal endpoints will be tested for equivalence in both study arms by means of chi-square statistics derived from contingency tables, ordinal variables by linear statistics. All tests will be performed via stratification for participating center and lymph node status. For visualization, Kaplan-Meier survival curves (in case of censored secondary endpoints) or mosaic plots (in case of contingency tables) will be used.

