4.2 Secondary Endpoints

- Resection rate
- rate of sphincter preservation
- tumor regression
- cumulative incidence of local and distant recurrences
- overall survival
- toxicity
- quality of life

5. Reasons for early Cessation of Trial Therapy

If toxicity requires therapy interruption of > 2 weeks, the patient will be removed from the study for toxicity reasons.

Throughout the study, patients may be subject to medical assessment and review of compliance before continuing in the study. Patients must continue to meet the inclusion and exclusion criteria during the study, including restrictions related to contraception, if applicable, and medication use. Noncompliant patients may be discontinued from the study.

Every patient will be informed that participation in the study is voluntary and that consent can be withdrawn at any time without the need to provide reasons, and without disadvantage or prejudice.

6. Objectives and Entire Statistical Section (Including Endpoints)

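### Section 6.4.3 assigns Kaplan-Meier curves to recurrence endpoints defined as cumulative incidences, so the recurrence percentages read from them would be too high

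*Protocol*

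**What the plan says.** The endpoint is named twice. Protocol Section 4.2 lists "cumulative incidence of local and distant recurrences", and Section 6.1 lists "cumulative incidence of local relapses and distant metastasis". Death is not part of this endpoint in either place.

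The method is in Section 6.4.3: "Censored secondary endpoints will be analyzed analogously to the method described in Section 6.4.1". Section 6.4.1 tests DFS with a log-rank statistic stratified by center and nodal status: the hypothesis "is based on the 'intent-to-treat' population assessed by log-rank statistics". It reports a hazard ratio with a 95% confidence interval and adds: "The primary endpoint will be visualized by Kaplan-Meier survival curves". Section 6.4.3 repeats the choice of curve for secondary endpoints: "For visualization, Kaplan-Meier survival curves (in case of censored secondary endpoints".

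The DFS definition in Section 6.1 counts "death of the patient" as an event. Its two censoring reasons, end of the study and patient dropout, are written for DFS. The protocol does not say how a death without recurrence is handled when recurrence alone is the endpoint.

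**The concern.** Kaplan-Meier suits DFS because death is a DFS event and leaves no competing event. For recurrence alone it recognises only two outcomes, event or censored. A patient who dies without recurrence is then treated as someone who could still recur later. One minus Kaplan-Meier estimates the recurrence risk in a hypothetical population without deaths. Cumulative incidence is the share of randomized patients who actually recur, and one minus Kaplan-Meier cannot fall below it. It exceeds it as soon as deaths precede later recurrences.

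The named quantity and the only named estimator therefore do not match. At stake are the recurrence percentages the trial would report. In relative terms local recurrence is the more exposed, because it can be rare compared with the events that compete with it. The 5-year follow-up in Section 2.1 leaves time for the gap to grow.

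**Working it through.** The protocol states no recurrence incidence and no rate of death without recurrence, so there is no figure to reproduce. Both checks below assume constant cause-specific hazards.

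**Check 1: assumed true 5-year incidences.** Let c be the true cumulative incidence of the recurrence and d that of the competing event. All values of c and d are assumptions.

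- Total cumulative hazard: H = -ln(1 - c - d)
- Recurrence part: s = H × c / (c + d)
- One minus Kaplan-Meier with competing events censored: 1 - exp(-s)

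For c = 6% and d = 20%: H = -ln(0.74) = 0.3011; s = 0.3011 × 0.06/0.26 = 0.0695; 1 - exp(-0.0695) = 6.7%.

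| Recurrence | True c | Competing d | 1 - KM | Excess (points) | Relative |
|---|---|---|---|---|---|
| Local | 6% | 20% | 6.7% | 0.7 | 12% |
| Local | 6% | 35% | 7.4% | 1.4 | 24% |
| Local | 10% | 25% | 11.6% | 1.6 | 16% |
| Distant | 30% | 10% | 31.8% | 1.8 | 6% |
| Distant | 30% | 15% | 32.9% | 2.9 | 10% |

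**Check 2: anchored to the protocol's DFS.** Section 6.2 gives 3-year DFS of 74.9% (control) and 82% (experimental). The total hazards are -ln(0.749)/3 = 0.0963 and -ln(0.82)/3 = 0.0662 per year. The share q of DFS events that are deaths without recurrence is not given and is assumed to lie between 5% and 40%. Every other DFS event is treated as a recurrence, which is a simplification. With total hazard L:

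- 1 - KM = 1 - exp(-(1 - q) × L × t)
- Cumulative incidence = (1 - q) × (1 - exp(-L × t))

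| Arm | q | Year | 1 - KM | Cumulative incidence | Excess (points) |
|---|---|---|---|---|---|
| Control | 10% | 3 | 22.9% | 22.6% | 0.3 |
| Control | 20% | 3 | 20.6% | 20.1% | 0.6 |
| Control | 20% | 5 | 32.0% | 30.6% | 1.4 |
| Control | 40% | 5 | 25.1% | 22.9% | 2.2 |
| Experimental | 20% | 5 | 23.3% | 22.5% | 0.7 |
| Experimental | 40% | 5 | 18.0% | 16.9% | 1.1 |

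Over both arms and all shares from 5% to 40%, the excess for any recurrence is 0.1-0.9 points at 3 years and 0.2-2.2 points at 5 years.

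**Between arms.** Section 6.4.4 sets a 5-point limit on the increase in grade V toxicity. Suppose competing events differ by that much while true recurrence is equal in both arms. By the formula of check 1:

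- Local 6%, competing 20% against 25%: 6.7% against 6.9%, a spurious difference of about 0.2 points.
- Local 6%, competing 35% against 40%: 7.4% against 7.7%, about 0.3 points.
- Distant 30%, competing 10% against 15%: 31.8% against 32.9%, about 1.0 point.

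In check 2, with an equal share q in both arms, the excesses at 5 years differ by 1.4 - 0.7 = 0.7 points at q = 20% and by 2.2 - 1.1 = 1.1 points at q = 40%.

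For comparison, the simple binomial standard error of a difference with 600 per arm is sqrt(2 × p × (1 - p)/600): 1.4 points at p = 6% and 2.6 points at p = 30%.

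**The case against.** Several points against the concern stand, and they limit it.

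- The protocol never states that deaths are censored. This follows from applying Kaplan-Meier to an endpoint that excludes death. It is the natural reading, but an inference.
- Section 6.4.3 names Kaplan-Meier for visualization, and its reference to 6.4.1 leads first to the log-rank test and hazard ratio. Nowhere is it written that reported percentages will be one minus Kaplan-Meier. Against this, percentages are ordinarily read from such curves, and no other estimator is named for an endpoint called a cumulative incidence.
- An SAP may exist and could settle the estimator. But the protocol does not leave the method open: it assigns one that does not fit, and an SAP that followed it would carry the mismatch forward.
- All secondary analyses are declared explorative, and the sizes above rest on assumed rates.

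A reader might infer that the comparison of recurrence between arms is itself invalid. The documents do not support that. The comparison specified is a stratified log-rank test with a hazard ratio, and with deaths censored both validly compare cause-specific hazards. The 5-point grade V limit is a ceiling that must not be crossed, not an expected difference. Even at that ceiling the artefact in the curves is about 0.2-1.0 points, inside one standard error of the arm difference.

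**Conclusion.** The point holds for the incidence estimates and curves only. The protocol names a cumulative incidence and assigns an estimator that overstates it. This is a mismatch in what is written, not a missing detail.

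Under the assumed 5-year rates, the excess is about 0.7-1.4 points for a true local recurrence of 6% with 20-35% competing events, and about 2-3 points for a true distant recurrence of 30% with 10-15% competing deaths. At 3 years, anchored to the stated DFS, it stays below one point for any recurrence. These sizes depend on constant hazards and on competing-event rates that the protocol does not give. The direction does not.

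It would be wrong to extend this to the primary result. DFS counts death as an event, so its test, its Kaplan-Meier curves and the sample size are untouched.

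**What to change.** Amend Section 6.4.3 as follows:

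- Estimate and plot local and distant recurrence with the Aalen-Johansen cumulative incidence estimator, with death without that recurrence as the competing event.
- Keep the stratified log-rank test and hazard ratio for these endpoints, labelled as cause-specific comparisons.
- Restrict Kaplan-Meier to DFS and overall survival.

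Gray's test could be added to compare cumulative incidences directly. It is optional, because it answers a different question from the cause-specific log-rank test and its absence is not an error.

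The cost is a few sentences of text and analysis code. Recurrence and death are already recorded for DFS, so no new data are needed.

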6.4.4 Safety Analyses

The safety analyses are based on toxicity grades I to V. In general, due to the known neurotoxicity of oxaliplatin a trend to higher toxicity grades is assumed, however, the following limits must not be exceeded:

- not more than 5 percent absolute increase in grade V toxicity in the experimental compared to the control arm
- not more than 5 percent absolute increase in grade V toxicity in the experimental compared to the control arm
- not more than 20 percent absolute increase in grade IV toxicity in the experimental compared to the control arm
- not more than 30 percent absolute increase in grade III toxicity in the experimental compared to the control arm

The initial safety analysis will be conducted six months after study begin, if at least 50 patients in each arm have completed therapy, otherwise at that time point at which at least 50 patients in each arm have completed therapy. Thereafter, safety analyses will be carried out annually and refer to the patient cohort as described in Section 6.3.

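### Section 6.4.3 announces an equivalence test for nominal secondary endpoints but names a chi-square test of difference without a margin, so a non-significant result could be misread as equivalence

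*Protocol*

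**What the plan says.** Protocol section 6.4.3 sets the method for secondary endpoints that are not time-to-event: "Nominal endpoints will be tested for equivalence in both study arms by means of chi-square statistics derived from contingency tables, ordinal variables by linear statistics". It adds "All tests will be performed via stratification for participating center and lymph node status". No equivalence margin, two one-sided test procedure or confidence-interval rule accompanies this. The nominal endpoints listed in 6.1 include R0 resection and sphincter preservation, and no expected rate is given for either.

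Three other places bear on the reading:

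- Section 6.1 words the study null as follows: "The null hypothesis of this study is that there is no statistically significant difference between the experimental and the control arm". Section 6.4.1 instead takes equal DFS in the two arms as the null for the log-rank test.
- Section 6.4.2 says "interim analyses have to be restricted on the confirmatory analysis of secondary endpoints referring to treatment safety", whereas 6.4.3 says "All analyses of secondary endpoints including interim safety analyses are of explorative nature, in particular, no adjustment for multiple testing will be performed".
- The only numerical limits on a between-arm difference are the toxicity limits in 6.4.4, for example "not more than 5 percent absolute increase in grade V toxicity in the experimental compared to the control arm".

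**The concern.** The sentence in 6.4.3 gives the test an aim that the test cannot meet. A chi-square test on a contingency table, or a linear statistic for an ordinal variable, starts from equality and looks for evidence against it. Failing to find that evidence is compatible with equivalence, but also with a real difference that the trial was too small to detect. To show equivalence, one must name the largest difference that would be tolerated and exclude anything larger.

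Resectability and sphincter preservation are outcomes on which readers will want to know whether intensified treatment has a cost. If the protocol describes the analysis as a test for equivalence, a reader of the results could take p > 0.05 as evidence that there is none.

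Two related wordings blur the inference further. The null in 6.1 describes the outcome of a test, not a state of the two arms. The interim safety analyses are called confirmatory in one section and explorative in the next. That label matters because 6.4.2 ties these analyses to stopping the study.

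**Working it through.** **The protocol's own figure.** The protocol states no power, margin or sample size for nominal endpoints. The only stated size is for the primary test: "about 1200 patients (600 in each arm) will be necessary to achieve a power of 80% at 5% significance level with the log-rank test". A check of that figure:

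- HR = ln(0.82)/ln(0.749) = 0.687.
- Freedman's formula gives 228 events.
- The mean 3-year failure probability is (0.251 + 0.18)/2 = 0.2155, and 228/0.2155 = 1058.
- Allowing for 5% violations in each arm, 1058/0.95² = 1172, within 3% of 1200.

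A Lachin-Foulkes calculation with 3 years of accrual, 2 years of minimum follow-up and 5% crossover in each arm gives about 1144, so 1200 is somewhat conservative. The check serves only to justify using 600 per arm below.

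**Inputs for the illustration.** From the protocol: n = 600 per arm (6.2). Assumed: control rates of 50% to 95%, a true loss of 5 points, a two-sided 5% level for secondary tests, and no stratification. The protocol states 5% only for the primary test.

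**Formula.** For control rate p₁, experimental rate p₂ = p₁ − 0.05 and p̄ = (p₁ + p₂)/2:

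- SE₀ = √[2 p̄(1 − p̄)/n]
- SE₁ = √{[p₁(1 − p₁) + p₂(1 − p₂)]/n}
- P(non-significant) = 1 − Φ[(0.05 − 1.96·SE₀)/SE₁]

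**Two cases in full.**

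- 90% vs 85%: p̄ = 0.875, SE₀ = 0.01909, SE₁ = 0.01904. (0.05 − 0.03742)/0.01904 = 0.66, so P = 25.4%.
- 70% vs 65%: p̄ = 0.675, SE₀ = 0.02704, SE₁ = 0.02700. (0.05 − 0.05300)/0.02700 = −0.11, so P = 54.4%.

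**Range.** Section 2.1 prints 800 per arm beside a total of about 1200, so that size is shown as well.

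| Control vs experimental | Non-significant, 600 per arm | Non-significant, 800 per arm |
|---|---|---|
| 95% vs 90% | 9.1% | 3.3% |
| 90% vs 85% | 25.4% | 14.3% |
| 85% vs 80% | 37.5% | 25.0% |
| 80% vs 75% | 45.5% | 33.2% |
| 70% vs 65% | 54.4% | 43.0% |
| 50% vs 45% | 58.9% | 48.3% |

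With 570 per arm (5% lost), the 90% and 70% rows become about 28% and 56%. Exact binomial enumeration at 600 per arm agrees closely: for 95% vs 90% it gives power 0.914, so 8.6% non-significant.

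**What an equivalence rule would do.** Take an illustrative margin of ±5 points, rates of 70% vs 65% and 600 per arm, so that the true loss equals the margin. In simulation the chi-square test is non-significant 54% of the time, while a rule requiring the 90% CI to lie inside the margin is met 3% of the time.

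If the arms are truly equal, the power of that rule is 2Φ(0.05/SE − 1.645) − 1, with SE = √[2p(1 − p)/600]. At p = 0.70, SE = 0.02646 and the power is 19%. It is about 40% at 80%, 79% at 90% and 98% at 95%. The half-width of the 95% CI over these rates runs from about 5.2 points (70%) to 2.5 points (95%). So the planned size could support an equivalence statement at that margin only where the rate is high.

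**The case against.** The strongest reply is that 'equivalence' here simply means equality. Section 6.4.1 has equal DFS as its null, the chi-square test named in 6.4.3 is the ordinary test of homogeneity, and the missing margin is what one expects if no equivalence test was intended. The English is loose elsewhere too. This reading is plausible. On it the method is right and the word is wrong, but the sentence still needs the same correction.

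A reader might infer more than the protocol supports:

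- *That the plan will declare equivalence whenever p > 0.05.* It attaches no decision rule, level or conclusion to these tests and calls them explorative. The sentence permits a misreading; it does not prescribe one.
- *That safety stopping is weakened.* The limits in 6.4.4 are absolute increases, worded without a significance test, so miss rates of a chi-square test do not describe them. Toxicity is also graded I to V, so it would fall under the ordinal part of the sentence.
- *That a 5-point loss is missed at one particular rate.* Any such figure depends on control rates that the protocol does not give. Limited power for an explorative endpoint is in itself no error.

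Nor is the lack of a named interval for nominal endpoints a defect on its own, since that is commonly left to the SAP. For censored secondary endpoints, 6.4.3 refers back to 6.4.1, which includes the hazard ratio with its 95% CI. What stands against the plan is the mismatch between stated aim and named test, and the conflicting status of the safety analyses. The explorative label waives multiplicity adjustment; it does not make a difference test able to show equivalence.

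**Conclusion.** The concern holds as a minor point of wording and interpretation. As written, 6.4.3 claims a test for equivalence that its chi-square statistic cannot deliver, and nothing elsewhere in the protocol supplies a margin. If non-significance were taken as equivalence, a true 5-point loss would pass unnoticed in about 9% to 59% of trials with 600 per arm, or about 3% to 48% with 800, over control rates from 95% down to 50%. These ranges rest on the assumed rates, loss and two-sided 5% level, and they ignore stratification by centre and nodal status.

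The contradiction between 6.4.2 and 6.4.3 on the status of the interim safety analyses is plain from the text and needs no calculation. The null in 6.1 is badly worded but harmless to the primary test, because 6.4.1 states it properly. The effect is confined to how secondary endpoints are interpreted.

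**What to change.** - **6.4.3:** say that nominal endpoints are compared for differences between the arms, in place of the reference to equivalence. Report the risk difference with its 95% CI for each, and state that a non-significant result is not evidence of equivalence.
- **If an equivalence statement is wanted for an endpoint:** base it only on a confidence interval lying inside a margin fixed before analysis.
- **6.4.2 and 6.4.3:** give the interim safety analyses one status, confirmatory or explorative, and use it in both sections.
- **6.1:** restate the null as equal DFS in both arms, in line with 6.4.1.

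The cost is a few sentences and one interval per endpoint from data already being collected, with no added patients or procedures. The downside is that some results that might have been reported as no difference will have to be reported as inconclusive.
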